15.1.6 Not fulfilling the ICHD-3 Diagnostic Criteria for CM/MOH

The ICHD-3 diagnostic criteria for CM is either 1, or 0 if the criteria are not fulfilled, or the criteria are fulfilled, respectively, based on the criteria in Section 3.9. Similar to the ICHD-3 diagnostic criteria for MOH, 1 if the criteria are not fulfilled and 0 if the criteria are fulfilled.

For Weeks 1-4 criteria testing, 28-days period eDiary data are used for derivations. If the CM criteria is not fulfilled, set to ‘1’, otherwise set to ‘0’. Similar for the MOH criteria diagnosis. Similar procedure for the Weeks 5-8, and Weeks 9-12 criteria. For the “CM nor MOH” criteria, for each of the 4-week periods, a participant is classified as “not fulfilled” if both the CM and MOH criteria are not fulfilled, and as “fulfilled” if at least one of the CM or MOH criteria are fulfilled.

For Weeks 1-12 criteria testing, 3 x 28-days period eDiary data are used for derivations. If participant not fulfills the CM criteria in all three 28-days periods, set to ‘1’, otherwise set to ‘0’. If any of the 28-days periods included in the calculation is missing after prorating, the status of CM will be derived based on the available values. Similar for the MOH criteria diagnosis. For the “CM nor MOH” criteria, a participant is set to ‘1’ (“not fulfilled”) if both these CM and MOH criteria are not fulfilled, and set to ‘0’ (“fulfilled”) if at least one of the CM or MOH criteria are fulfilled.

Note that the IHS ICHD-3 Guideline stated in [Panel 3](#) (Section 3.6) can be interpreted as it would be enough to be free from CM during just one of the three 28-days periods to be defined as “not fulfilled”. The Weeks 1-12 criteria testing used for this trial is thus more conservative than the IHS ICHD-3 Guideline stated in [Panel 3](#).

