3.9.2 Definition of MOH during the trial

Panel 4 IHS ICHD-3 Guidelines for MOH

- A. Headache occurring on ≥ 15 days/month in a patient with a pre-existing headache disorder
- B. Regular overuse for >3 months of one or more drugs that can be taken for acute and/or symptomatic treatment of headache
- C. Not better accounted for by another ICHD-3 diagnosis

Regular overuse is defined either on:

- 10 days of use/month or more for >3 months of ergotamine, triptan, opioid (butorbital in US), or combination of analgesics
- 15 days of use/month or more for >3 months of non-opioid analgesics (paracetamol [acetaminophen], acetylsalicylic acid, NSAIDs)

In [Panel 4](#) above, the IHS ICHD-3 Guidelines for MOH are stated and used to confirm the MOH diagnosis at the screening visit.

During the trial, to evaluate whether a participant continues to overuse acute migraine medication, the eDiary data will be used for a specific post-baseline 4-week period (28-day period) only and the steps below will be followed:

Check acute migraine medication overuse in the reported month.

Count the number of days on which a medication was taken to treat a headache for each pre-defined acute migraine medication in the reported month (28-days period).

If the participant meets any of the following criteria in the reported month, the participant is considered as overusing acute migraine medication, used as “MOH” in the endpoint definitions. N is the number of monthly days.

- $N \geq 10$ days with either ergotamine, or $N \geq 10$ days with triptan
- $N \geq 10$ days with combination of two or more drug classes among ergotamine, triptan, opioid analgesic and non-opioid analgesics
- $N \geq 10$ days on which combination analgesics are taken.
- $N \geq 15$ days on which a non-opioid analgesic (paracetamol, acetylsalicylic acid, NSAIDs, analginum, antipyrine, tolfenamic acid) is taken. The overuse could be with a single non-opioid analgesic or with several of them.

4 Analysis Sets

The following analysis sets will be used to analyse and present the data:

- *all-participants-screened set (APSS)*
- *all-participants-randomized set (APRS)* – all randomized participants
- *all-participants-treated set (APTS)* – all participants in the APRS who received an infusion of the IMP in the Placebo-controlled Period
- *full-analysis set (FAS)* – all participants in the APTS who had a valid baseline assessment and at least one valid post-baseline 4-week assessment of MMDs in Weeks 1-12

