8.4 Substance Use

Substance use (alcohol, tobacco, caffeine, marijuana consumption) throughout the trial will be collected at all visits until the Week 12 Visit/Withdrawal Visit (if the participant withdraws during the placebo-controlled period). Substance use will be summarized by treatment group and visit based on APTS.

9 Exposure

All randomized participants are expected to receive one single infusion of the IMP after BI in the Placebo-controlled Period and one infusion of the IMP in the Open-label Period. For each infusion visit, information related to infusion will be summarized by actual treatment group for the Placebo-controlled Period and by actual treatment sequence in the Open-label Period:

- BI completed as planned
- infusion completed as planned
- infusion temporarily interrupted
- infusion lasted longer than 30 (+15) minutes
- duration of infusions (includes duration of any infusion interruptions)
- duration of temporary interruptions.

All infusion data will be listed for each period separately. Additionally, treated participants whose infusion took more than 45 minutes and participants who had their infusion interrupted will be listed by treatment group, infusion start date/time and end date/time, infusion related reactions, and reasons if any.

The summaries will be based on the APTS and APTS-OL, respectively.

10 eDiary Compliance

For the Screening period, the Placebo-controlled Period and the Open-label Period, the rate of days where the eDiary has been missed within each 4-week interval will be summarized and presented by 4-week interval and treatment group/treatment sequence. Furthermore, the number of participants missing 7 days or more and 14 days or more in a 28-day period will be presented by 4-week interval and treatment group/treatment sequence.

The summaries will be based on the FAS for the Placebo-controlled Period and based on APTS-OL for the Open-label Period.

11 Efficacy

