	
the eptinezumab group compared to the placebo group, this is considered to be a conservative approach.
 
A hypothetical strategy is used to handle use of disallowed anti-CGRP medication other than eptinezumab as preventive migraine medication. This will better reflect clinical practice, since it is not standard practice to prescribe two different anti-CGRP treatments simultaneously.
	

Table 4 Key Secondary Endpoints and Analyses

Key Secondary Endpoint	Population Level Summary	Primary Analysis	Sensitivity Analysis
Change from baseline in the number of MMDs (Weeks 1-12) Change from baseline in number of MHDs (Weeks 1-4) Change from baseline in MHDs (Weeks 1-12)	The mean difference in the change of number of MMDs or MHDs from baseline between participants on eptinezumab and placebo	MMRM	pMI + MMRM
Not fulfilling the ICHD-3 diagnostic criteria for CM nor MOH (Weeks 1-4) Not fulfilling the ICHD-3 diagnostic criteria for CM nor MOH (Weeks 1-12)	Odds ratio of participants not fulfilling the ICHD-3 diagnostic criteria for CM nor MOH between participants on eptinezumab and placebo	Logistic Regression	-
Change from baseline in average Daily Pain assessment score (Week 1-2)	The mean difference in the change from baseline in average Daily Pain assessment score between participants on eptinezumab and placebo	ANCOVA	ANCOVA on the days without taking any acute migraine medications
Change from baseline in monthly days with acute migraine medication use (Weeks 1-4) Change from baseline in monthly days with acute migraine medication use (Weeks 1-12)	The mean difference in the change from baseline in acute migraine medication use between participants on eptinezumab and placebo	MMRM	pMI + MMRM

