The ICHD-3 diagnostic criteria for CM and/or MOH will be checked at Baseline, Week 4, Week 8, and Week 12 according to the IHS ICHD-3 criteria in the Section 3.9 and the endpoints, including the Weeks 1-12 endpoint, will be derived based on the description in the Section 15.1.6. Missing data after pro-rating will not be used in the analysis. Same manner will be applied to the derivation of Weeks 13-24 endpoint in Open-label Period. The treatment effect of these two endpoints will be analysed using logistic regression with baseline MMDs as a covariate, and treatment group, country and previous treatment failures (≤ 2 , > 2) as categorical variables based on the eDiary data collected over Weeks 1-4 and over Weeks 1-12 separately. The logistic regression model will be fitted using the maximum likelihood (ML) method and the logit link function. The odds ratios for EPTI compared to PBO will be estimated from the model and presented with p-values based on the likelihood ratio test and 95% CIs based on the profile likelihood. In case of convergence, sparsity or separation issues, refer to Section 15.15 for pooling rule.

Change from baseline in average Daily Pain assessment score (Week 1-2)

Daily pain assessment data will be collected in the headache eDiary via the question “*What was the worst pain intensity of this headache today?*”. The pain intensity assessment is collected on a 3-point scale: Mild (score = 1), Moderate (score = 2) and Severe (score = 3).

For each day, the daily pain assessment score will be derived by averaging the worst pain intensity over all headaches of that day. For days on which no headache takes place during the relevant period, the daily pain score will be given as a score of 0. The average daily pain score will be calculated using the daily pain assessments collected during Weeks 1-2. For data

handling details, see Section 15.1.7. Change from baseline in average Daily Pain will be analysed using an ANCOVA with the average Daily Pain at baseline as a covariate and including treatment group, country, and previous treatment failures, as categorical variables. The estimates will be presented with p-values and 95% CIs.

Change from baseline in monthly days with acute migraine medication use (Weeks 1-4)

Change from baseline in monthly days with acute migraine medication use (Weeks 1-12)

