11.4.4 Sensitivity Analysis of the Key Secondary Endpoints

For the key secondary endpoints change from Baseline in MMDs (Weeks 1-12), change from baseline in MHDs (Weeks 1-4, Weeks 1-12), and change from baseline in monthly days with use of acute migraine medication (Weeks 1-12), pMI will be conducted similarly to the first sensitivity analysis described for the primary endpoint, see Section 11.3.4.

For the change from baseline in average Daily Pain Assessment (Weeks 1-2), the sensitivity analysis will be conducted using the same ANCOVA model in Section 11.4.2 but we will derive the average daily pain assessment score on the days without taking any acute migraine medications. For data handling details, see Section 15.1.7.

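### For being free of both CM and MOH over Weeks 1-12, a missing month is scored as if it were a clean month, and no sensitivity analysis tests this

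*SAP*

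**What the plan says.** SAP 15.1.6 scores the Weeks 1-12 CM component as 1 under this condition: "If participant not fulfills the CM criteria in all three 28-days periods". Otherwise it is 0. If any period "is missing after prorating, the status of CM will be derived based on the available values". MOH follows the same rule, and the combined endpoint is 1 only when both components are 1. A month is missing when fewer than 14 of its 28 diary days are reported (SAP 15.1.1).

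The FAS (SAP 4) requires only "at least one valid post-baseline 4-week assessment of MMDs in Weeks 1-12", so one valid month is enough to enter the analysis.

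The endpoint is tested at Step 6 (SAP 11.2) by logistic regression (SAP 11.4.2). That section also states, for the open-label version: "Same manner will be applied to the derivation of Weeks 13-24 endpoint in Open-label Period". The separate CM and MOH secondary endpoints for Weeks 1-12 (SAP 11.5) use the same derivation.

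Table 4 has a dash in the sensitivity-analysis column for the two CM/MOH endpoints. SAP 11.4.4 says "pMI will be conducted similarly to the first sensitivity analysis described for the primary endpoint", but lists only migraine days, headache days and acute-medication days. The exploratory re-analyses in SAP 11.4.5 vary the migraine-day definition, not the handling of missing months. The protocol (16.8.5) leaves key secondary sensitivity analyses to the SAP.

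**The concern.** Working from the available months is reasonable for an average, as in the responder derivation of SAP 15.1.2, because dropping a month does not push an average in a fixed direction. An all-of-three rule behaves differently: with fewer observed months there are fewer chances to fail. Someone lost after a clean Month 1 is recorded as a 12-week success, although Estimand 2b is defined across Weeks 1-12.

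Two things are at stake. The reported 12-week rates can be too high in both arms. If missingness differs between arms, the odds ratio also shifts in favour of the arm with more missing months, on an endpoint that is alpha-controlled and gates Steps 7 to 9. Steps 1 to 5 are not touched by this rule.

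**Working it through.** **The logic.** Write 1 for a clean month, 0 for a month fulfilling the criteria and M for a missing month. Under SAP 15.1.6:

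| Months 1, 2, 3 | Score under the SAP | Score if M is coded clean |
|---|---|---|
| 1, 1, 1 | 1 | 1 |
| 1, 1, M | 1 | 1 |
| 1, M, M | 1 | 1 |
| 1, 0, M | 0 | 0 |
| 0, M, M | 0 | 0 |

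The last two columns always agree. One observed failing month still gives 0; the rule matters only when every observed month is clean.

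**Inputs.** The documents give no expected rate, correlation or 12-week missingness for this endpoint, so there is no figure of the plan's to reproduce. The 5% non-contribution allowance (Protocol 16.12) concerns the primary analysis. The only figure taken from the plan is 270 per arm.

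Assumptions: monthly success 50% (eptinezumab) and 35% (placebo); an exchangeable latent-normal model with correlation 0.6; missingness unrelated to response.

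**Formulas.** Let P1, P2 and P3 be the probabilities that one, two or three months are all clean, and let d be the share of an arm with incomplete data.

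- Only Month 1 observed: SAP rate = (1 − d)·P3 + d·P1.
- Half with one month, half with two: (1 − d)·P3 + (d/2)·(P1 + P2).
- Only Month 3 missing: (1 − d)·P3 + d·P2.
- Missing counted as fulfilled: (1 − d)·P3.

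Numerical integration gives P2 = 0.3524 and 0.2138, and P3 = 0.2786 and 0.1550. The true odds ratio is (0.2786/0.7214)/(0.1550/0.8450) = 2.10.

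**Worked case, 15% eptinezumab and 5% placebo with only Month 1.**

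- Eptinezumab: 0.85 × 0.2786 + 0.15 × 0.50 = 0.312.
- Placebo: 0.95 × 0.1550 + 0.05 × 0.35 = 0.165.
- Odds ratio: (0.312/0.688)/(0.165/0.835) = 2.30 from unrounded values.

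| Incomplete, eptinezumab/placebo | SAP rates, only Month 1 seen | OR, only Month 1 seen | OR, half one and half two months | OR, only Month 3 missing | OR, missing = fulfilled |
|---|---|---|---|---|---|
| 5%/5% | 29.0%, 16.5% | 2.07 | 2.08 | 2.10 | 2.08 |
| 10%/10% | 30.1%, 17.5% | 2.03 | 2.06 | 2.09 | 2.06 |
| 15%/5% | 31.2%, 16.5% | 2.30 | 2.24 | 2.17 | 1.80 |
| 5%/15% | 29.0%, 18.4% | 1.81 | 1.90 | 2.01 | 2.37 |

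At correlation 0.7 the true odds ratio is 2.03, and the only-Month-1 results are 2.19 (15%/5%) and 1.81 (5%/15%).

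**No true effect.** Take monthly success 45% in both arms and correlation 0.65, so P3 = 0.2485. At 15%/5% with only Month 1:

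- Rates: 0.85 × 0.2485 + 0.15 × 0.45 = 0.2787, and 0.95 × 0.2485 + 0.05 × 0.45 = 0.2585.
- Spurious difference: 2.0 points.
- With 270 per arm the standard error is 0.0381, so the test statistic is centred at 0.53 and the two-sided type I error is about 0.083.

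At 8%/5% the difference is 0.6 points and the error about 0.053. With equal missingness there is no bias under the null.

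**The case against.** **The SAP calls its rule conservative.** SAP 15.1.6 notes that ICHD-3 could be read so that freedom from CM in one of the three periods is enough, and that the trial's rule is stricter. On that reading, one clean month already counts as not fulfilling CM. But the note compares the rule with the guideline for CM. Having chosen the all-three rule, the plan gives no reason to relax it only for participants with missing months.

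**Missing data are said not to be used.** SAP 11.4.2 says that data still missing after prorating are left out. Read alone, this could mean dropping incomplete participants. The same passage sends the Weeks 1-12 derivation to 15.1.6, which says otherwise, so the available-months reading is the better one.

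**The illustration uses unfavourable patterns.** This stands in part. If only Month 3 is missing, the odds ratios are 2.17 and 2.01. If Month-1 failures drop out three times as often as Month-1 successes, they are 2.21 (15%/5%) and 1.97 (5%/15%), and the null type I error at 15%/5% falls to about 0.057. Nothing in the documents points to a 10-point imbalance: there is one infusion, retention is encouraged, and missing diary data are expected to be mostly sporadic.

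**Missingness will be visible.** SAP 10 says "the number of participants missing 7 days or more and 14 days or more in a 28-day period will be presented" by treatment group, and withdrawals are tabulated by arm (SAP 6). A reader could suspect a problem from these tables but could not see its effect on the endpoint.

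**Replacing the derivation is late.** SAP 3.0 followed the classification meeting. This is a fair point, and the fallback below meets it.

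**Conclusion.** The concern holds. For this endpoint a missing month is scored exactly like a clean one, and no planned analysis tests the consequence. That follows from the text and needs no assumption.

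The size does rest on assumptions: monthly rates of 50% and 35%, correlation 0.6 to 0.7, the missing shares, and missingness unrelated to response. Under them, low and balanced missingness raises each rate by one or two points and pulls the odds ratio slightly towards 1 (2.10 to 2.07 or 2.03). A 10-point imbalance with only Month 1 observed moves it to 2.30 or 1.81. The direction cannot be told from the documents; more missingness on placebo would work against eptinezumab. The primary endpoint is unaffected. This should be corrected, but it does not undermine the trial.

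**What to change.** 1. In SAP 15.1.6, keep the score of 0 once any observed month fulfils CM or MOH.
2. If all observed months are clean but at least one is missing, treat the status as undetermined and multiply impute it. Impute monthly CM and MOH status directly, or impute headache days, migraine days and the class-specific medication counts of SAP 3.9.2. Those counts include "days with combination of two or more drug classes among ergotamine, triptan, opioid analgesic and non-opioid analgesics", which the planned imputation of total acute-medication days cannot supply. Derive the endpoint in each imputed dataset and combine the logistic regressions by Rubin's rule.
3. Add to Table 4 and SAP 11.4.4 an analysis counting a missing month as fulfilled. Label it a bound: with unequal missingness it errs in the opposite direction (1.80 at 15%/5% and 2.37 at 5%/15%, against 2.10).
4. Report by arm how many participants scored 1 rest on one, two and three valid months.
5. Carry the same handling to the separate CM and MOH endpoints and to Weeks 13-24.

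If the primary derivation can no longer be changed, add items 2 to 4 as sensitivity analyses and reporting.

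The cost is SAP text and some new imputation programming. No new data are needed, and under item 2 the reported 12-week rates will be slightly lower.

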15.1.7 Average Daily Pain Assessment Score

Average daily pain assessment score will be calculated based on days from a headache where at least one of the days of the headache had pain assessment reported for Week 1, Week 2, Weeks

1-2 and any given 4-week period, regardless of the number of reported eDiary days with the period. If a day is a reporting day with missing daily pain assessment and it is not a day on which no headache takes place, then this day will be imputed based on the average daily pain scores from the other day(s) of the same headache. Otherwise, it will be treated as a missing day.

For the sensitivity analysis, only reported eDiary days without taking any acute migraine medications will be included in the calculation of the average daily pain score in the respective period. If a day is a reporting day with missing daily pain assessment and it is not a day on which no headache takes place, then this day will be imputed based on the average daily pain scores from the other day(s) without taking any acute migraine medications of the same headache. Otherwise, it will be treated as a missing day. If the participant has no such days in the Week 1, Week 2, Weeks 1-2 period, or in any 4-week period, applying a conservative approach, the value will be set to 3 (“Severe”) for that period.

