11.2 Testing Strategy

In all statistical tests, the null hypothesis of equal treatment effect in the two treatment groups will be tested against the two-sided alternative hypothesis of different treatment effect in the two treatment groups. The testing will be done hierarchically, in a sequence of a maximum number of 9 steps where the different null hypotheses are tested until an endpoint fails to reach significance. For each step in this sequence, the treatment effect will be tested using a two-sided test on a 5% significance level and testing will only continue to the next step if all prior effects in the hierarchy were found to have p-values below the specified significance level, thus ensuring protection of the type 1 error.

Step 1

Test the primary endpoint change from baseline in the number of MMDs (Weeks 1-4) for EPTI compared to PBO, using a significance level of 0.05.

Step 2

Test the key secondary endpoint change from baseline in the number of MMDs (Weeks 1-12) for EPTI compared to PBO, using a significance level of 0.05.

Step 3

Test the key secondary endpoint change from baseline in the number MHDs (Weeks 1-4) for EPTI compared to PBO, using a significance level of 0.05.

Step 4

Test the key secondary endpoint change from baseline in the number MHDs (Weeks 1-12) for EPTI compared to PBO, using a significance level of 0.05.

Step 5

Test the key secondary endpoint not fulfilling the ICHD-3 diagnostic criteria for CM nor MOH (Weeks 1-4) for EPTI compared to PBO, using a significance level of 0.05.

Step 6

Test the key secondary endpoint not fulfilling the ICHD-3 diagnostic criteria for CM nor MOH (Weeks 1-12) for EPTI compared to PBO, using a significance level of 0.05.

Step 7

Test the key secondary endpoint change from baseline in average Daily Pain assessment score (Weeks 1-2) for EPTI compared to PBO, using a significance level of 0.05.

Step 8

Test the key secondary endpoint change from baseline in monthly days with acute migraine medication use (Weeks 1-4) for EPTI compared to PBO, using a significance level of 0.05.

Step 9

Test the key secondary endpoint change from baseline in monthly days with acute migraine medication use (Weeks 1-12) for EPTI compared to PBO, using a significance level of 0.05.

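### SAP 15.1.7 can be read as leaving headache-free days out of the average Daily Pain score (Step 7), which conflicts with the score of 0 that SAP 11.4.2 gives them

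*SAP*

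**What the plan says.** Step 7 of the fixed sequence in SAP 11.2 reads "Test the key secondary endpoint change from baseline in average Daily Pain assessment score (Weeks 1-2) for EPTI compared to PBO, using a significance level"; the level given there is 0.05. Testing stops at the first endpoint that is not significant, so Steps 8 and 9 (acute medication days) depend on it.

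SAP 11.4.2 defines the score. Headache pain is rated 1, 2 or 3 (mild, moderate, severe), and the ratings are averaged over the headaches of a day. It then states: "For days on which no headache takes place during the relevant period, the daily pain score will be given as a score of 0". The daily scores are averaged over Weeks 1-2, and the change from baseline goes into an ANCOVA. For the rest, the reader is sent on: "handling details, see Section 15.1.7".

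SAP 15.1.7 says the average is "calculated based on days from a headache where at least one of the days of the headache had pain assessment reported", and that this applies "regardless of the number of reported eDiary days with the period". A reporting day that lacks a rating and is not headache-free is imputed from the other days of the same headache. The next sentence is "Otherwise, it will be treated as a missing day". The score of 0 does not appear in this section.

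The sensitivity analysis in 15.1.7 uses reported eDiary days without acute medication. It sets the value to 3 if a participant has no such day in the period.

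**The concern.** The section that governs data handling names headache days as the basis of the average. It then gives a rule for days without a rating whose fallback is a missing day. The rating question is asked about a particular headache, so a headache-free day never has a rating. It is also excluded from the imputation. Read literally, the only clause left for it is the fallback, and it drops out. Under 11.4.2 the same day enters as 0.

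The two readings measure different things. With zeros, the score is a burden measure that falls when headache days become fewer. Without them, it is the average intensity given that a headache is present. A treatment that removes headache days but leaves the intensity of the rest unchanged would show an effect on the first and none on the second. Participants with no headache at all in Weeks 1-2, the best outcomes on this endpoint, would have no value under the second reading and would leave the ANCOVA. If that reading were carried into the sensitivity analysis, they could be counted as having no usable day and be set to 3, the worst score.

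**Working it through.** The documents give no effect, SD or power for Daily Pain, so there is no stated figure to reproduce. The check is to score the same diary both ways.

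**Inputs from the documents.** Scores 0 to 3 (SAP 11.4.2); a 28-day baseline (SAP 3.1); a 14-day post-baseline window; 15 to 26 headache days in screening (Protocol 5.3).

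**Assumed for illustration.** Complete diaries, the headache-day counts within those limits, and mean pain on headache days.

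**Formulas.** Reading A (11.4.2): sum of daily scores / all reported days. Reading B (15.1.7 taken literally): sum of daily scores / headache days.

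**Score in Weeks 1-2, mean pain 2 on headache days**

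| Headache days of 14 | A | B |
|---|---|---|
| 0 | 0 | undefined |
| 4 | 4 × 2 / 14 = 0.57 | 2.00 |
| 7 | 7 × 2 / 14 = 1.00 | 2.00 |
| 10 | 10 × 2 / 14 = 1.43 | 2.00 |
| 14 | 14 × 2 / 14 = 2.00 | 2.00 |

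**Change from baseline, mean pain 2 throughout, 7 of 14 headache days after dosing**

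| Baseline headache days of 28 | A | B |
|---|---|---|
| 15 | 1.00 − 15 × 2 / 28 = −0.07 | 2.00 − 2.00 = 0.00 |
| 20 | 1.00 − 20 × 2 / 28 = −0.43 | 0.00 |
| 26 | 1.00 − 26 × 2 / 28 = −0.86 | 0.00 |

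The sign can also differ. Take 20 of 28 days at mean pain 2.0, then 6 of 14 days at 2.3. A gives 6 × 2.3 / 14 − 1.43 = −0.44. B gives 2.3 − 2.0 = +0.30.

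**Between-arm consequence.** A small simulation put both scores through an ANCOVA adjusted for baseline only (270 per arm, 400 runs). Assumed: a typical headache-day probability of 72% at baseline and 60% on placebo in Weeks 1-2, with variation between participants in frequency and intensity.

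| Assumed eptinezumab effect | A: difference, rejection rate | B: difference, rejection rate |
|---|---|---|
| Headache-day probability 55%, intensity unchanged | −0.09, 74% | 0.00, 4% |
| Headache-day probability 50%, intensity unchanged | −0.18, about 100% | 0.00, 4% |
| Frequency unchanged, underlying intensity lower by 0.1 | −0.055, 34% | −0.088, 97% |

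The choice of reading can therefore decide Step 7 in either direction, depending on what the drug does. The rejection rates belong to the assumed diary patterns and do not forecast this trial.

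**The case against.** The strongest reply is that 15.1.7 does not contradict 11.4.2 and only supplements it. Much of this stands:

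- The zero rule in 11.4.2 is explicit. The opening of 15.1.7 does not restrict the average to headache days exclusively; it can be read as saying which headache days are usable.
- The imputation rule sets headache-free days apart, which fits their already having a 0.
- The fallback clause cannot be fully literal, because it would then also make days with a recorded rating missing.
- The sensitivity analysis uses reported eDiary days. Under SAP 3.7 these include days with a confirmed absence of headache.
- Scoring a headache-free participant as severe is implausible as an intention.

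These points show that zeros are the likely intention. They do not make the text safe, because the reader must infer the rule against the wording of the section that 11.4.2 names for data handling. Neither Protocol 16.8.4 nor SAP chapter 18 settles it.

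Three stronger conclusions might be drawn, and the documents do not support them:

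- A reader might infer that the SAP fixes two different values for Step 7. It does not; it has one probable meaning and one literal meaning.
- A reader might infer from 11.4.2 that unreported days score 0. SAP 3.7 separates confirmed headache-free days from missing eDiary days, so this does not follow.
- A reader might count the lack of a minimum number of days as part of the conflict. Neither section sets a minimum, and 15.1.7 says openly that none applies. That is a prespecified choice on which statisticians can differ.

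**Conclusion.** The point holds as an ambiguity in the derivation of a tested key secondary endpoint. SAP 11.4.2 gives headache-free days a 0, while SAP 15.1.7, read literally, leaves them out. In the illustration the same participant changes by −0.43 or 0.00, and a participant without headache in Weeks 1-2 scores 0 or has no value. The readings agree only in special cases, such as headache on every day, or unchanged frequency and intensity.

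The diary patterns are assumptions. The changes shown are for single participants and are not treatment effects, since the placebo arm also receives the brief educational intervention and may change too. Without an SD for Daily Pain in the documents, no standard error or power for Step 7 can be derived from them. The conclusion does not need one: it rests on the two texts and on the fact that Step 7 gates Steps 8 and 9. The correction should be made, and it does not touch the primary endpoint or Steps 2 to 6.

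**What to change.** Amend SAP 15.1.7 as follows:

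1. Reported eDiary days with a confirmed absence of headache score 0 and count in the denominator, at baseline and in Weeks 1-2. The other periods listed in the section follow the same rule.
2. The same applies in the sensitivity analysis, restricted to days without acute medication. The value 3 is then assigned only when no eligible day exists, and never because a participant had no headache.
3. The missing-day clause covers only unreported days and headache days whose headache has no usable pain rating.

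The cost is a few sentences and a check that the program matches them. Version 3.0 of the SAP made corrections of this kind to the PGIC direction and the TSQM-9 scoring before unblinding. If treatment codes are already open, the report should state which derivation was programmed and that it was fixed beforehand.

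Separately and optionally, the SAP could set a minimum number of reported days for Weeks 1-2 or give a reason for having none. The price of a minimum would be some additional missing values on this endpoint.
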